Appendix

Data pre-processing

CGM baseline glucose algorithm estimated using the algorithm provided below. Nocturnal CGM iAUC calculated as the area under the curve of CGM glucose minus baseline between 12 midnight and 4am.

Total number of steps is set to missing if the number of assessment days is less than 5.

Imputation Overview

Missing data is imputed within allocated treatment group.

HbA1c, fasting glucose concentration, fasting insulin concentration and steps-per-day are imputed on log scale and back transformed for analyses on the original scale.

Log of the total steps-per-day is analysed with an offset of log of number of days assessed.

Baseline variables are used for imputing all variables.

All variables within an assessment period are used per assessment period, diet-discontinue (no vs yes), average compliance (per period) and repeated measures of each variable are also included.

For example imputing 4 month (log) HbA1c uses all baseline variables, all 4 month variables, the binary diet-discontinue variable, the four month average compliance and the 12 month (log) HbA1c variable.

All variables are imputed with predictive mean matching except the compliance and diet-discontinue variables for which ordinal and logistic regressions are used respectively.

```

## Imputation methods
{
  library(mice)
  mice.fit <- mice(
    data=imp.data
    , m=1, maxit=0
    , blocks=var.list
    , visitSequent=var.list
    , formulas=fm.list
  )
  # mice.fit$loggedEvents
  method.<-mice.fit$method
  method.[names(method.) == 'm4.compliance'] <- (
    "~ I((
      0.5*as.numeric(as.character(m0.5))*((ice.grp == 'Completer') + (ice.grp == 'Discontinue diet')*(drop.out.time >= 0.5))
      + 0.5*as.numeric(as.character(m1))*((ice.grp == 'Completer') + (ice.grp == 'Discontinue diet')*(drop.out.time >= 1))
      + 1*as.numeric(as.character(m2))*((ice.grp == 'Completer') + (ice.grp == 'Discontinue diet')*(drop.out.time >= 2))
      + 1*as.numeric(as.character(m3))*((ice.grp == 'Completer') + (ice.grp == 'Discontinue diet')*(drop.out.time >= 3))
      + 0.5*as.numeric(as.character(m3.5))*((ice.grp == 'Completer') + (ice.grp == 'Discontinue diet')*(drop.out.time >= 3.5))
      + 0.5*as.numeric(as.character(m4))*((ice.grp == 'Completer') + (ice.grp == 'Discontinue diet')*(drop.out.time >= 4))
    )/14/4)"
  )
  method.[names(method.) == 'm12.compliance'] <- (
    "~ I((
      4*as.numeric(as.character(m8))*((ice.grp == 'Completer') + (ice.grp == 'Discontinue diet')*(drop.out.time >= 8))
      + 4*as.numeric(as.character(m12))*((ice.grp == 'Completer') + (ice.grp == 'Discontinue diet')*(drop.out.time >= 12))
    )/14/8)"
  )
  method.
}
rm(mice.fit)
}
ls()

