Appendix: Imputation overview and details (page 14)

ABBREVIATIONS

AUC	Area under the curve
AUSDRISK	The Australian type 2 diabetes risk assessment tool
BMI	Body mass index
CGM	Continuous glucose monitoring
CP	Current best practice
DSMC	Data safety monitoring committee
HbA1c	Glycated haemoglobin
iAUC	Incremental area under the curve
M0, M4, M12	M0 = baseline; M4 = 4 month; and M12 = 12 month assessments
SAP	Statistical analysis plan
TRE	Time restricted eating
T2DM	Type II diabetes mellitus
WOW	Study: What Or When to eat to reduce the risk of type 2 diabetes

PREFACE

This statistical analysis plan (SAP) describes the planned analyses and reporting for the WOW study to compare the impact of time restricted eating (TRE) versus current best practice (CP) in adults at high risk of 2 diabetes. The purpose of this SAP is to outline the considerations and the pre-specified analyses for the WOW study.

The project is funded by the Medical Research Future Fund Preventative and Public Health Grant MRF1200555 awarded to [name].

This study has been approved by the Central Adelaide Local Health Network Human Research Ethics Committee (#14023).

Study Objectives

Primary

To determine whether TRE is not inferior to current practice guidelines (CP) in dietetics to reduce HbA1c at 4 months, in individuals at high risk of developing T2DM.

Secondary

Secondary aim of this study is to assess the short (4 month) and long term (12 month) effect of TRE on HbA1c and glucose metabolism.

Exploratory

The exploratory aims of this study are to assess:

- Adherence of TRE vs CP over 4 and 12 months.
- The impact of TRE vs CP at 4 and 12 months on cardio-metabolic health.
- The impact of TRE vs CP at 4 months on 24-h profiles of glycaemia by CGM

Study Outcomes

Primary objective: 4 months

Primary efficacy outcome: Change in glycated haemoglobin (HbA1c)

Secondary efficacy outcomes

- Change in fasting glucose, insulin, and HOMA-IR
- Nocturnal glucose CGM AUC (midnight to 4 am)

Secondary objective: 12 months

Secondary efficacy outcomes

- Change in HbA1c
- Change in fasting glucose concentrations, insulin concentrations, HOMA-IR

Exploratory objective: Adherence

- Adherence: Self-reported (Assessed: Month 0.5, 1, 2, 3, 3.5, 4, 8, 11.5, 12)
- Diet records (energy, macronutrient intake) by diary (Assessed M0, M4, M12)
- Meal timing / eating window by self-reported meal timing, time stamped food photos (Assessed M0, M4, M12)

Exploratory objective: Cardiometabolic

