Mean difference in HbA1c between treatment groups.

Intercurrent Events

- Discontinuation of diet for any reason (including: lifestyle, dislike of diet and non-related medical adverse events).
- Unable to attend four-month HbA1c assessment due to reasons unrelated to diet (including moving overseas or interstate).
- Drop-out of study with reason unspecified.

Intercurrent Event Strategies

- Due to the intervention being dietary modification it is assumed that efficacy outcomes are strongly tied to compliance, thereby intercurrent event strategies are defined as whether individuals were able to continue the diet or not.
- Treatment policy will be assumed for individuals with diet discontinuation by assuming zero compliance thereafter.
- Hypothetical policy will be assumed for individuals who left the study (without diet discontinuation) by imputing compliance as if they had continued with the study.
- For individuals with unspecified drop-out reason diet discontinuation (yes/no) will be imputed within treatment group, then compliance will be imputed accordingly (ie treatment or hypothetical policy).

Sensitivity Analysis: Worst case

- All individuals in the TRE group with drop-out reason unknown will be assumed that they had discontinued the diet.
- All individuals in the CP group with drop-out reason unknown will be imputed as if they had continued the diet.

Sensitivity Analysis: Complete case

- No imputation, the analysis will only include individuals with HbA1c assessed at 4 months. This analysis assumes the missing data are missing completely at random.

Statistical Considerations

Error control: For the primary outcome the difference between TRE and CP will be assessed for non-inferiority. If the non-inferiority null is rejected then superiority will be tested. Two-sided 95% confidence intervals will be reported (ie one-sided 2.5% type I error rate). No multiple test adjustments will be made for secondary and exploratory outcomes.

Analysis Sets: Analyses of efficacy outcomes at 4 and 12 months (HbA1c, fasting glucose, insulin, HOMA-IR) will include all randomized individuals via multiple imputation. This process also requires physical activity and compliance data, as such analyses of these outcomes will also include all randomized individuals. Analyses of all other (exploratory) outcomes will be complete case analyses.

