Covariate adjustment: All comparisons of treatment effect will include adjustment for stratification factors (site and baseline HbA1c as a continuous variable) and for sex as it is known that men are higher risk for diabetes.

Descriptive Statistics: A CONSORT flow diagram will present the number of individuals who participated in online screening, and clinic visits 0-3 (Figure 1). Descriptive summary statistics will be reported for baseline characteristics of all individuals who were randomized.

Statistical Methods

Primary Outcome

The primary analysis of the primary outcome is a covariate adjusted linear regression of differences in HbA1c at 4 months, adjusting treatment group (TRE vs CP), baseline HbA1c (continuous), site (Adelaide vs Melbourne) and sex (male vs female).

Non-inferiority will be concluded if upper 95% confidence interval of the effect estimate of the difference between groups (TRE – CP) is less than 0.1%. If non-inferiority is concluded then superiority may also be concluded if the upper 95% confidence interval excludes a between group difference of 0%.

This analysis will be performed in all randomized individuals with individuals using multiple imputation using chained equations within treatment groups and combined using Rubin's rules. The variables used in the multiple imputation are HbA1c (M0, M4 & M12), age, sex, site, fasting glucose (M0, M4 & M12) and insulin (M0, M4 & M12) concentrations, steps per day (M0, M4 & M12), nocturnal glucose CGM AUC (M0, M4), reason for dropout (related/unrelated to diet) and average compliance (first 4 months, and 4 to 12 months). Compliance will be imputed as per the intercurrent event strategies and the average compliance calculated over each period. Imputation will use multiple chained equations (*mice* R package), details of which are presented in the Appendix.

Secondary & Exploratory Outcomes

Treatment effect for the change in HbA1c at 12 months and other outcomes required for the multiple imputation of the primary outcome (assessed at 4 and/or 12 months) will be assessed using the same methodology as for the primary outcome, i.e. generalized linear regressions with multiple imputation for missing data.

Other outcomes will be analysed using generalized linear regressions adjusting for the same covariates, however these analyses will be complete case analyses.

Safety Outcomes

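### The compliance formulas zero the whole reporting interval in which a participant stops the diet, and the 4 to 12 month formula leaves out the month 11.5 report

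*SAP*

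**What the plan says.** The Intercurrent Event Strategies section of the SAP gives the rule: "Treatment policy will be assumed for individuals with diet discontinuation by assuming zero compliance thereafter". The Primary Outcome section carries it into the data: "Compliance will be imputed as per the intercurrent event strategies and the average compliance calculated over each period". The periods are given there as "average compliance (first 4 months, and 4 to 12 months".

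The Exploratory objective on adherence lists the reports: "Adherence: Self-reported (Assessed: Month 0.5, 1, 2, 3, 3.5, 4, 8, 11.5, 12".

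The Appendix code (Imputation methods) builds `m4.compliance` from the reports at months 0.5, 1, 2, 3, 3.5 and 4, with terms such as "1*as.numeric(as.character(m2))*((ice.grp == 'Completer') + (ice.grp == 'Discontinue diet')*(drop.out.time >= 2". It builds `m12.compliance` from two reports only, "4*as.numeric(as.character(m8))*((ice.grp == 'Completer') + (ice.grp == 'Discontinue diet')*(drop.out.time >= 8" and "4*as.numeric(as.character(m12))*((ice.grp == 'Completer') + (ice.grp == 'Discontinue diet')*(drop.out.time >= 12".

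On use of the result, the Analysis Sets paragraph says: "This process also requires physical activity and compliance data, as such analyses of these outcomes will also include all randomized individuals". The Imputation Overview makes the average compliance of each period a predictor for that period's missing values.

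**The concern.** Each weight in the code equals the time since the previous report used, so each report stands for the interval that ends at it. The condition on `drop.out.time` then keeps or removes that interval as a whole. A participant who stops between two reports loses the months on diet since the last one, although the stated rule sets only later time to zero. Before month 4 an interval is at most one month. After month 4 it is four months, half of the averaging period.

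Month 11.5 is a separate matter. The 0 to 4 month formula uses the parallel month 3.5 report, but the 4 to 12 month formula does not use month 11.5. A report of adherence made half a month before the end therefore cannot count for anyone who stops afterwards.

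Adherence of TRE against CP over 4 and 12 months is a stated exploratory aim. An error that affects only discontinuers creates an arm difference when discontinuation is unequal. The same averages feed the imputation of HbA1c, glucose and insulin.

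**Working it through.** **Inputs.** The weights, divisors and conditions come from the Appendix code, and the report times from the adherence objective. Assumptions: a full report scores 14, the participant is fully adherent while on diet, and `drop.out.time` is the actual stopping time *t*.

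**Reproducing the plan's scaling.** The weights 0.5 + 0.5 + 1 + 1 + 0.5 + 0.5 = 4 and 4 + 4 = 8 match the divisors, so a full complier scores 1.00 in each period. This confirms that each report represents the interval ending at it.

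**Coded value against the stated rule.** With zero only after *t*, the average should be *t*/4 for months 0 to 4 and (*t* − 4)/8 for months 4 to 12.

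| Period | Stop at month | Coded | Zero only after stopping | Gap |
|---|---|---|---|---|
| 0–4 | 1.5 | 0.250 | 0.375 | 0.125 |
| 0–4 | 2.9 | 0.500 | 0.725 | 0.225 |
| 0–4 | 3.9 | 0.875 | 0.975 | 0.100 |
| 4–12 | 6 | 0 | 0.250 | 0.250 |
| 4–12 | 7.9 | 0 | 0.4875 | 0.4875 |
| 4–12 | 10 | 0.500 | 0.750 | 0.250 |
| 4–12 | 11.9 | 0.500 | 0.9875 | 0.4875 |

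The gap is zero when *t* falls exactly on a report that the code uses. With 10/14 compliance while on diet, the two largest 4 to 12 month gaps become 0 against 0.348 (stop at 7.9) and 0.357 against 0.705 (stop at 11.9).

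**Mean gap for a uniform stopping time (assumption).** For interval widths *w* in a period of length *T*, a stop falls in a given interval with probability *w*/*T* and loses *w*/(2*T*) on average. The mean loss is therefore Σ*w*²/(2*T*²).

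- Months 0 to 4: Σ*w*² = 4 × 0.25 + 2 × 1 = 3, and 3/32 = 0.094. The maximum approaches 1/4 = 0.25.
- Months 4 to 12: Σ*w*² = 16 + 16 = 32, and 32/128 = 0.25. The maximum approaches 4/8 = 0.50.

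The true mean is 0.50 in both cases, so about 19% and 50% of real adherence is lost.

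**Month 11.5.** With weights 4, 3.5 and 0.5, someone adherent at 11.5 who stops before 12 scores (4 + 3.5)/8 = 0.9375 rather than 0.50. Over all stopping times this step alone changes the mean loss little: (16 + 12.25 + 0.25)/128 = 0.223 against 0.25. Proration is needed for the rest.

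**Arm level (assumed rates).** If 20% of one arm and 10% of the other stop between months 4 and 12, the spurious difference in mean adherence is (0.20 − 0.10) × 0.25 = 0.025.

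**Other codings of `drop.out.time`.** If it is rounded up to the next visit in the code, a stop at month 6 is coded 0.50 against 0.25, and the error is an overstatement. If it holds the last visit on diet, the stop at 6 is coded 0, as under the actual time.

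**The case against.** The strongest reply is that the code applies one visit-level convention to everybody. A completer's months 4 to 8 also rest on the month 8 report alone, and a visit after stopping does lie after discontinuation, so scoring it zero is consistent with the rule. This explains the code but does not reconcile it. The weight carries that zero back over up to four months on diet, and the SAP describes an average over the period, not a visit score.

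Several points on this side stand:

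- `drop.out.time` is not defined. A reader might infer that the adherence of discontinuers is known to be understated. The SAP does not support that, because rounding up reverses the sign.
- If the variable holds the last visit on diet, and that visit is one the formula uses, proration returns 0 or 1 and changes nothing.
- Proration also fails if it multiplies a zero reported after stopping.
- The 0.25 applies only to people who stop between months 4 and 12, with uniform times and full prior adherence. The arm-level figure of 0.025 rests on assumed rates.

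A reader might also infer that the primary non-inferiority result is compromised. The documents do not support that. The Imputation Overview imputes 4-month HbA1c from the 0 to 4 month average, where the error is smaller, alongside all baseline and 4-month variables and a separate diet-discontinuation indicator. The 4 to 12 month average is not in the list given for 4-month HbA1c and can act only indirectly, through imputed 12-month values. Four-month attrition is described as close to 10%.

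**Conclusion.** The concern holds as a mismatch between the stated rule and the printed code for anyone who stops between reports, and as an unexplained omission of month 11.5. The omission matters under actual-date or last-visit coding of `drop.out.time`, where the 4 to 12 month value is 0.50 instead of at least about 0.94 for a fully adherent person who stops between 11.5 and 12.

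The mean understatements of 0.25 and 0.094 hold if the variable is the actual stopping time, stopping is uniform and prior adherence is full. Their direction is not established until the variable is defined.

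The consequence is for the exploratory TRE against CP adherence comparison and the 12-month imputations. The effect on the primary HbA1c estimate cannot be computed from the SAP and is probably small. The change is worth making before analysis, but it does not call the primary analysis into question.

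**What to change.** 1. Add month 11.5 to `m12.compliance`, with weights 4, 3.5 and 0.5 for `m8`, `m11.5` and `m12`, each with its own condition on `drop.out.time`. This matches the use of month 3.5 before month 4.
2. Define `drop.out.time` as the actual date of stopping the diet where recorded, and state how it is set otherwise.
3. In both formulas, replace each all-or-nothing condition for discontinuers by the share of the interval on diet, `pmin(pmax(drop.out.time - start, 0), width)/width`. Apply it to compliance while on diet, meaning the last on-diet report or an imputed on-diet value, and not a zero reported after stopping. A stop at 11.9 then gives (4 + 3.5 + 0.4)/8 = 0.9875, as the rule requires.
4. If stopping dates were not recorded, state the visit-level convention in the Intercurrent Event Strategies section so that text and code agree.

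The cost is a few lines of code on reports already scheduled, and `m11.5` must be among the imputed variables if it is not already. The small downside is that compliance in the part interval before stopping comes from the last or imputed report.

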## Imputation per treatment group
M <- 100; N.iter <- 100
for (group. in 0:1) {
  library(mice)
  mice.fit <- mice(
    data=imp.data[imp.data$group == group.,]
    , m=M, maxit=N.iter
    , blocks=var.list
    , visitSequent=var.list
    , formulas=fm.list
    , method=method.
    , print=1
  )
  mice.fit$loggedEvents
  # plot(mice.fit)

  if (group. == 0) mice.fit.g0 <- mice.fit
  if (group. == 1) mice.fit.g1 <- mice.fit
  rm(mice.fit)
}
rm(group., M., N.iter)
rm(var.list, method., fm.list, imp.data)
ls()

#####
## Primary Analysis
#####

## HbA1c at 4 months
library(mice)
fm. <- "lm(exp(hbA1c.log.v2) - exp(hbA1c.log.v1) ~ group + sex + state + exp(hbA1c.log.v1))"
output <- summary(pool(with(
  data = rbind(mice.fit.g0, mice.fit.g1)
  , expr = eval(parse(text=fm.))
))); output
grp.est <- output$estimate[2]
grp.est.se <- output$std.error[2]
grp.est.df <- output$df[2]
grp.est.p <- output$p.value[2]
if (grp.est.p < 0.001) grp.est.p <- '<0.001'
if (grp.est.p >= 0.01) grp.est.p <- format(round(grp.est.p, 2), nsmall=2)
if (grp.est.p < 0.01 & grp.est.p >= 0.001) grp.est.p <- format(round(grp.est.p, 3), nsmall=3)
paste(
  'ITRE - CP: '
  , format(round(grp.est, 2), nsmall=2), ' ['
  , format(round(grp.est - qt(1-0.05/2, df=grp.est.df)*grp.est.se, 2), nsmall=2), ', '
  , format(round(grp.est + qt(1-0.05/2, df=grp.est.df)*grp.est.se, 2), nsmall=2), ']; p='
  , grp.est.p, sep=' '
); rm(grp.est, grp.est.se, grp.est.df, grp.est.p, output, fm.)

```

```

#####
## Secondary outcome example analyses
#####

## HbA1c at 12 months
library(mice)
fm. <- "lm(exp(hba1c.log.v3) - exp(hba1c.log.v1) ~ group + sex + state + exp(hba1c.log.v1))"
output <- summary(pool(with(
  data = rbind(mice.fit.g0, mice.fit.g1)
  , expr = eval(parse(text=fm.))
))); output
grp.est <- output$estimate[2]
grp.est.se <- output$std.error[2]
grp.est.df <- output$df[2]
paste(
  'iTRE - CP: '
  , format(round(grp.est, 2), nsmall=2), ' ['
  , format(round(grp.est - qt(1-0.05/2, df=grp.est.df)*grp.est.se, 2), nsmall=2), ', '
  , format(round(grp.est + qt(1-0.05/2, df=grp.est.df)*grp.est.se, 2), nsmall=2), ']'
  , sep=' '
); rm(grp.est, grp.est.se, grp.est.df, output, fm.)

## Other Secondary outcomes will also adjust for their baseline and HbA1c at baseline
## Glucose at 4 months
library(mice)
fm. <- "lm(exp(glu.log.v2) - exp(glu.log.v1) ~ group + sex + state + exp(glu.log.v1) + exp(hba1c.log.v1))"
output <- summary(pool(with(
  data = rbind(mice.fit.g0, mice.fit.g1)
  , expr = eval(parse(text=fm.))
))); output
grp.est <- output$estimate[2]
grp.est.se <- output$std.error[2]
grp.est.df <- output$df[2]
paste(
  'iTRE - CP: '
  , format(round(grp.est, 2), nsmall=2), ' ['
  , format(round(grp.est - qt(1-0.05/2, df=grp.est.df)*grp.est.se, 2), nsmall=2), ', '
  , format(round(grp.est + qt(1-0.05/2, df=grp.est.df)*grp.est.se, 2), nsmall=2), ']'
  , sep=' '
); rm(grp.est, grp.est.se, grp.est.df, output, fm.)

rm(mice.fit.g0, mice.fit.g1, MNAR.type)
ls()

```

CGM code

```
CGM.baseline.fn <- function(y, t, threshold=1, smooth.range=4*2*3 + 1, iter=8) {
  # y = time series observations
  # t = time of observations
  # smooth.range = #obs/hr * both directions * duration (hr) + 1 (median)
  # threshold = deviations from local mean (Note that threshold can be defined as residual SD
  #, but not needed here.)
  # iter = number of iterations for

  ## Ensure y is correctly ordered
  y <- y[order(t)]

  ## Ensure no two consecutive readings with the same value the same
  cond. <- c(F, y[-1] == y[-length(y)])
  y[cond.] <- y[cond.] + 1/100/sum(cond.)
  rm(cond.)

  ## Generate baseline smooth y without large deviations (large defined as > threshold)
  smoothed.y <- y
  signals <- rep(0, length(y))
  for (it. in 1:iter) {
    # it. <- 1
    library(zoo)
    smoothed.y[signals != 0] <- NA
    smoothed.y <- rollapply(
      data=smoothed.y
      , width=smooth.range
      , partial=T
      , by.column = FALSE
      , FUN=function(x) { return(mean(x, na.rm=T))})
    smoothed.y <- na.fill(smoothed.y, "extend")

    ## When smoothed.y too high due to NA imputing reduce by threshold
    smoothed.y[y < smoothed.y - threshold] <- smoothed.y[y < smoothed.y - threshold] - threshold
    smoothed.y <- rollmean(smoothed.y, k=ceiling((smooth.range - 1)/2), fill='extend')

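### The CGM baseline code re-smooths its own output and never returns to the raw readings, so daytime meal peaks raise the midnight-to-4am baseline used for the nocturnal iAUC

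*SAP*

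**What the plan says.** The SAP's Study Outcomes section lists as a secondary outcome "Nocturnal glucose CGM AUC (midnight to 4 am"). The imputation list under Statistical Methods, Primary Outcome, also says AUC. The Appendix (Data pre-processing) gives the only operational definition, and it is incremental: "Nocturnal CGM iAUC calculated as the area under the curve of CGM glucose minus baseline between 12 midnight and 4am".

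The baseline comes from `CGM.baseline.fn` (Appendix, CGM code). Its defaults are "threshold=1, smooth.range=4*2*3 + 1, iter=8", and a comment explains the window as "smooth.range = #obs/hr * both directions * duration (hr) + 1 (median"). That is 4 readings per hour and 3 h in each direction. The stated purpose of the loop is "Generate baseline smooth y without large deviations (large defined as > threshold").

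The working series is set equal to the raw readings once, before the loop. Inside the loop, flagged points are blanked with "smoothed.y[signals != 0] <- NA", the rolling mean takes "data=smoothed.y" as input, and a second smoother follows: "rollmean(smoothed.y, k=ceiling((smooth.range - 1)/2), fill='extend".

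**The concern.** Masking can remove a peak from a baseline only if it acts on the raw series. Here it acts on a series into which the peaks have already been averaged. Blanking the peak positions leaves the peak glucose that has spread to neighbouring readings, and each further pass carries it further from the meal.

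The two diets may change meal timing and daytime glucose. If the midnight-to-4am baseline responds to daytime eating, a daytime difference between arms can appear as a nocturnal one even when overnight glucose is identical. That would be bias in the treatment contrast for a secondary outcome, not only added noise.

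**Working it through.** **Inputs from the SAP.** Threshold 1; 8 passes; first window 4 × 2 × 3 + 1 = 25 readings; second window k = ceiling((25 - 1)/2) = 12 readings; 15-minute spacing (from the code comment). The SAP gives no figure for this outcome to reproduce.

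**Following the loop.**
1. Pass 1: no point is flagged yet, so the 25-point and 12-point means run over raw glucose with all meal peaks in it.
2. Passes 2 to 8: points flagged in the previous pass are blanked in the smoothed series, which is then smoothed twice more. Raw glucose is used only for flagging and for the downward adjustment, never again as the series being smoothed.
3. The series left after pass 8 is returned as the baseline.

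**Test traces (assumptions).** 14 days of 15-minute readings; glucose exactly 5.0 mmol/L from 00:00 to 06:00 in every scenario; gamma-shaped meal peaks, highest 1 h after the meal. Nocturnal iAUC = 4 h × mean(glucose - baseline) over 00:00-04:00, signed, on interior days. Because the overnight trace never changes, any movement in this value is artefact. The loop was run in R with the zoo package and re-coded in Python; the two agree to three decimals.

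**Pass by pass.** For +2 meals at 8:00, 12:30 and 18:30, the mean 00:00-04:00 baseline is 5.08, 5.18, 5.22, 5.25, 5.27, 5.29, 5.31, 5.33. It climbs at every pass. Final value: 4 × (5.00 - 5.33) = -1.32 mmol.h/L.

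**Nocturnal iAUC (mmol.h/L), overnight glucose identical throughout:**

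| Daytime pattern | As printed | Odd window only (k = 13) | Restart from raw | Restart and odd window |
|---|---|---|---|---|
| No meals | 0.00 | 0.00 | 0.00 | 0.00 |
| 8:00, 12:30, 18:30, +1 | -0.78 | -0.80 | -0.16 | -0.19 |
| same times, +2 | -1.32 | -1.36 | -0.29 | -0.32 |
| same times, +3 | -1.55 | -1.61 | -0.34 | -0.37 |
| 8, 11, 15 h, +2 | -1.05 | -1.02 | -0.02 | -0.03 |
| 8:00, 12:30, 20:00, +2 | -1.38 | -1.39 | -0.38 | -0.41 |

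Share of the level error removed by restarting: 1 - 0.29/1.32 = 78% (+2 meals), 1 - 0.38/1.38 = 72% (dinner at 20:00), 1 - 0.02/1.05 = 98% (early window). With autocorrelated noise (SD 0.3) the pattern holds: as printed, no meals +0.06, +2 meals -1.26, +3 meals -1.52. Two further independent codings gave -1.26 and -1.02 for three +2 meals.

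**Daytime-only change.** Halving only the breakfast and lunch peaks moves the printed code's value from -1.26 to -0.93 (+0.33) in one coding and by +0.30 in another. With the restart it moves by 0.00 in both.

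**Change in meal timing.** From 8:00/12:30/18:30 to 8/11/15 h at +2:
- as printed: -1.05 - (-1.32) = +0.27
- restart: -0.02 - (-0.29) = +0.27
- restart and odd window: -0.03 - (-0.32) = +0.29

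Moving dinner from 20:00 to 21:00 gives -0.04 as printed and +0.40 with restart and odd window (about -0.04 and +0.20 with noise).

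**The even window.** A 12-point window cannot be centred. In zoo it covers readings i-5 to i+6, half a reading (7.5 minutes) off centre per pass. Over 8 unmasked passes that is 8 × 0.5 = 4 readings, or 1.0 h. The table shows that making it odd leaves the leak in place.

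**The case against.** The strongest reply is that the listed outcome is a plain AUC, which needs no baseline, so the code might never touch it. This stands as a condition: the artefact reaches the secondary outcome only if the Appendix iAUC is what is analysed. But the Appendix gives the only operational definition, and it subtracts this baseline.

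A second reply is that a common level error largely cancels when change is compared between arms, and that the sizes rest on invented traces. A shift of 0.3 mmol.h/L over 4 h is a mean of 0.075 mmol/L, and the SAP gives no SD for this outcome against which to judge it. All of that is fair. It limits the claim about size but does not make the baseline what the code comment says it is.

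A third is that restarting from raw does not remove dependence on dinner time, and for a dinner moved from 20:00 to 21:00 the revised loop is worse than the printed one. This also stands. A 3-h half-window still reaches unmasked evening readings.

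Four stronger readings might be inferred and are not supported:
- **That the off-centre window causes the leak.** An odd width alone gives -1.36 against -1.32.
- **That the kernel of eight unmasked passes (SD 5.65 h) describes the algorithm.** It ignores the masking and the downward adjustment.
- **That 24-h iAUC is affected too.** The SAP does not say that it uses this baseline.
- **That the primary HbA1c result is biased.** Nocturnal CGM AUC is only one imputation variable, and no effect through it was quantified.

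**Conclusion.** The loop is wrong as written. It contradicts its own stated aim and makes the Appendix nocturnal iAUC depend on daytime eating. In the assumed traces the level error with three +2 mmol/L meals is about -1.0 to -1.3 mmol.h/L, and a change confined to breakfast and lunch produces a false nocturnal shift of about +0.3. The direction was the same in every trace with meals.

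These sizes assume 15-minute readings, a signed area and the meal shapes described. Whether the error differs by arm in the trial depends on how the diets change eating, which these traces cannot show. Restarting from raw removes most of the level error and the breakfast/lunch leak. It leaves about -0.1 to -0.4 with a dinner meal, and up to -0.85 with six eating occasions running to 21:00. It should not be presented as a complete cure.

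**What to change.** 1. Add `smoothed.y <- y` at the start of each pass, before blanking the points flagged in the previous pass. Every pass then smooths raw unflagged readings over the stated 3 h each side.
2. Before adopting it, run the revised function on traces with fixed overnight glucose and shifted dinner times, including frequent late eating. Report the remaining dependence, and revise the function further if it is not acceptable.
3. Give the second smoother an odd width (for example k = 13) to centre it. This is tidying and does not treat the leak.
4. State whether the secondary outcome and the imputation variable are AUC or iAUC, and use one term in Study Outcomes, Statistical Methods and the Appendix. State also whether 24-h iAUC uses this baseline.
5. Recompute the M0 and M4 CGM variables that use the baseline.

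The cost is one added line, one changed constant, a short simulation check, a wording correction and a rerun of CGM pre-processing. No new data are needed.
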